Considering a prior assumption that the EVT effect is largest in the patients with good imaging profile and treated within the shortest time window, we assume that the highest effect of EVT will be observed in G1A. Then the effects get decreased gradually in G1B, G2A, G2B, G3A, and the lowest effect will be observed in G3B. According to this adaptive design, when a most promising subgroup needs to be selected at the time of interim (or final) analysis, we will compare the GLR statistic among five cumulative groups, that is, G1A, G1A+G1B (i.e., Group 1), G1A+G1B+G2A, G1A+G1B+G2A+G2B (i.e., Group 1+Group 2), and G1A+G1B+G2A+G2B+G3A.

Primary analysis: The primary endpoint is the distribution of scores on the modified Rankin Scale (mRS) at day 90. The null hypothesis will be tested at the interim and final analysis using a normal approximation of the Wilcoxon-Mann-Whitney test (the GLR test). The principle of the intention to treat will be applied for the primary analysis. An additional analysis of the primary endpoint will be the same rank-based analysis comparing the 90-day mRs distribution between treatment groups while stratifying for prognostically important covariates. We will use the Generalized Cochran-Mantel-Haenszel test (CMH) to evaluate whether there is a uniform shift on the mRS distribution from one group to the other after stratification. The CMH test will be stratified by these variables used in the covariate adaptive randomization. For age, NIHSS, treatment time window, and CTP core volume, we will consider them as continuous variables in this adjusted analysis.

Power and sample size considerations Based on prior reported data, the following distributions were projected on the mRS at 90 days in EVT and MM groups for SELECT 2 in the overall population.

	mRS at day 90							Total
	0	1	2	3	4	5	6	
Endovascular group	4%	8%	12%	16%	19%	13%	28%	100%
Medical group	1%	4%	9%	14%	19%	10%	43%	100%

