This distribution corresponds to a standardized effect of 0.34 for the primary analysis. Based on these data, the fixed sample size for a non-adaptive design requires a total of 376 patients (188/arm) to have 90% power at an alpha of 5% (Wilcoxon-Mann-Whitney test); We add additional 184 patients for the adaptive design to reach a maximum sample size of 560. We will conduct two interim analyses when we reach the number of patients at 200 and 380. Through extensive simulation studies, we have shown that with 560 patients in total for the adaptive design, we will have around 91% power to test for a standardized effect size of 0.34 in the overall population (assuming homogeneous EVT effect across six disjoint groups) by controlling an overall (one-sided) Type I error rate at 2.5%.

Efficacy and futility bound At each analysis (two interim analyses and the final analysis), an efficacy bound will be set to decide if the study should be stopped for efficacy while controlling the overall (one-sided) Type I error rate at 2.5%. At each interim analysis, a futility bound will be set to decide if the study should continue recruitment in the overall group, shift accrual and testing to a subgroup, or stop the trial entirely. When the futility bound is crossed and the optimal subgroup is selected, the maximum analyzed sample size will not be fixed but a random variable (smaller than the fixed maximum sample size 560). Due to the reduction in the maximum number of patients available for analysis at the end of the study, our design allows

an easier futility stop after subgroup selection. Further details regarding efficacy and futility bounds at interim and final analyses is provided in Appendix B.

First interim analysis (n=200 randomized and completed 90-day follow-up): The null hypothesis is tested in the entire patient cohort:

1. If neither efficacy nor futility bound is crossed, the trial continues enrollment to the 2nd interim analysis.
2. If the efficacy bound is crossed, the trial stops and efficacy is declared in the overall cohort.
3. If the futility bound is crossed, the optimal subgroup is selected based on the GLR statistic and the null hypothesis is tested in this selected subgroup:
 - 3.1. If neither bound is crossed, the trial will continue with enrollment limited to the selected subgroup
 - 3.2. If the efficacy bound is crossed, the trial stops and efficacy is declared in the selected subgroup

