Appendix B. Efficacy and futility bounds for interim and final analysis

At the l th interim analysis, let W_i^l be the sum of the ranks of Rankin scores from the endovascular group in the patient subgroup Π_i , $j = 1, \dots, J$. In our trial, we defined $J = 6$ groups with Π_j denotes the entire patient population and Π_1, \dots, Π_5 denote the subgroups of G1A, G1A+G1B, G1A+G1B +G2A, G1A+G1B +G2A +G2B, G1A+G1B +G2A +G2B +G3A, respectively.

The standardized Wilcoxon statistic for patient subgroup Π_i is

$$Z_i^l = \left\{ W_i^l - \frac{n_i^l(n_i^l + n_{0i}^l + 1)}{2} \right\} / \left\{ \frac{n_i^l n_{0i}^l (n_i^l + n_{0i}^l + 1)}{12} \right\}^{1/2},$$

where, n_i^l and n_{0i}^l denote the numbers of patients enrolled into the endovascular group and medical management group at the l th interim analysis, respectively.

At the l th interim analysis, we will terminate the trial and claims efficacy for the endovascular group if the following efficacy bound is crossed, that is,

$$Z_j^l \geq b.$$

Otherwise, we will proceed to the subgroup selection if the following futility bound is crossed, that is,

$$\widetilde{Z}_j^l \leq \widetilde{b},$$

where

$$\widetilde{Z}_j^l = \left\{ W_i^l - \frac{n_i^l(n_i^l + n_{0i}^l + 1)}{2} - n_i^l n_{0i}^l \theta \right\} / \left\{ \frac{n_i^l n_{0i}^l (n_i^l + n_{0i}^l + 1)}{12} \right\}^{1/2}.$$

When the above criteria is satisfied, a subgroup \hat{I} with the largest value of Z_i^l for $i \neq J$ is chosen. The future enrollment of the trial will include patients of this subgroup only, while the maximum total sample size is still $N=560$.

Similar to testing the efficacy and futility in the entire population, at stage l' , we will terminate the trial and claim efficacy for the endovascular group in this selected subgroup if the following efficacy bound is crossed

$$Z_j^{l'} \geq b.$$

We may also terminate for futility if

$$\widetilde{Z}_j^{l'} \leq \widetilde{b}.$$

If neither the efficacy nor futility bound for the entire population ever occurs, the trial proceeds to the final stage and we terminate the trial and claim efficacy for the endovascular group if

$$Z_j^{l=3} \geq c.$$

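### The Appendix B Wilcoxon statistics use the no-ties variance on a heavily tied mRS, which makes the primary test slightly and needlessly conservative

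*Combined protocol and SAP*

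**What the plan says.** Appendix B gives "The standardized Wilcoxon statistic for patient subgroup" Πi as the endovascular rank sum W minus n(n+n0+1)/2, divided by {n·n0·(n+n0+1)/12}^(1/2). The futility statistic Z-tilde subtracts a further n·n0·θ and has the same denominator. Neither contains a tie term. Appendix B then sets θ = (z₁₋α + z₁₋β)/√(3N) = 0.0791 at N = 560, with bounds b = 2.604, b-tilde = −1.897 and c = 2.772.

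Section 6.1 projects the 90-day mRS (0 to 6) as "Endovascular group 4% 8% 12% 16% 19% 13% 28% 100" and "Medical group 1% 4% 9% 14% 19% 10% 43% 100" (percent). It adds: "This distribution corresponds to a standardized effect of 0.34 for the primary analysis". The fixed design "requires a total of 376 patients (188/arm) to have 90% power" with a Wilcoxon-Mann-Whitney test at alpha 5%. The adaptive design, with at most 560 patients, is said to have about 91% power while "controlling an overall (one-sided) Type I error rate at 2.5"%.

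The documents nowhere mention ties, midranks or a tie-corrected variance.

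**The concern.** The denominator n·n0·(n+n0+1)/12 is the null variance of the rank sum only when no two patients share a score. Here every patient falls into one of seven categories, and more than a third are expected in one of them. With midranks, ties reduce the variance of W, so dividing by the no-ties value pulls every Z towards zero.

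This is the confirmatory decision statistic at two interim analyses and the final analysis, and it also chooses the subgroup. If it is on a different scale from the one behind the bounds and the sample size, the design runs at lower size and power than it needs to. There is a practical risk as well. An analyst whose software applies the tie correction will get a different Z from one who follows Appendix B, and near a bound that could change the decision.

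**Working it through.** **Inputs.** The projected mRS distributions, 1:1 allocation, 376 patients, 90% power and two-sided 5% come from Section 6.1 (allocation from the enrollment and randomization text in Section 3). The bounds and θ come from Appendix B.

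**Effect and ties.**
- P(endovascular better) = 0.04×0.99 + 0.08×0.95 + 0.12×0.86 + 0.16×0.72 + 0.19×0.53 + 0.13×0.43 = 0.4906.
- P(tie) = 0.0004 + 0.0032 + 0.0108 + 0.0224 + 0.0361 + 0.0130 + 0.1204 = 0.2063.
- p = 0.4906 + 0.2063/2 = 0.59375, so p − 0.5 = 0.09375.
- Pooled shares: 2.5, 6, 10.5, 15, 19, 11.5 and 35.5%. Tie factor T = 1 − Σ(share³) = 1 − 0.0579 = 0.9421, and √T = 0.971.
- Medical-arm distribution in both arms: T = 1 − 0.0909 = 0.909.

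**Reproducing 376.** N = T(1.960 + 1.2816)²/{3(p − 0.5)²}.
- With ties: 0.9421 × 10.507/(3 × 0.008789) = 375.4, which is 188 per arm, or 376. This matches the plan.
- Without ties (T = 1): 398.5, about 6% higher.
- Appendix B's θ: (1.960 + 1.2816)/√(3×560) = 0.0791, reproduced by the no-ties formula.

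**Effect on the bounds.** The printed Z is 0.971 of the tie-corrected Z.
- b: 2.604/0.971 = 2.683; one-sided tail 0.0046 becomes 0.0037.
- c: 2.772/0.971 = 2.856; one-sided tail 0.0028 becomes 0.0021.
- A fixed test at nominal one-sided 0.025 has true size 0.0217 (pooled distribution) or 0.0199 (medical-arm distribution).

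**Fixed-design power at 376.**
- No-ties formula: Φ(0.09375√1128 − 1.960) = 88.3%.
- That formula treats the printed Z as having unit variance. Allowing for its smaller spread gives Φ{(0.09375√1128 − 1.960)/0.971} = 89.0%.
- Simulation from the projected distributions: 89.2–89.4% uncorrected, 90.3–90.5% corrected.

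**Adaptive design.** Simulated with midranks, the printed bounds, looks at 200, 380 and 560, and the subgroup shares in Section 6.1. There were 12,000–20,000 trials per scenario in one set and 15,000 in another. After subgroup selection, θ was taken at 560 minus the patients already in closed groups.

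| | Printed statistic | Tie-corrected |
|---|---|---|
| Type I error, across null distributions and sets | 1.4–1.7% | 1.9–2.3% |
| Power, projected effect | 90.5–90.9% | 92.4–92.5% |
| Mean N, projected effect | 356–360 | 346–348 |

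Monte Carlo error in the first set is about 0.1 point for type I error and 0.25 point for power. Its mean N under the null was 444–460, against 426 in Table 3. This implementation is therefore close to the plan's but not identical, and the contrast between columns is firmer than either column alone.

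**Effect on futility.** Correcting only the denominator of Z-tilde raises the chance of crossing the futility bound at the first interim from 51.5% to 53.9% under the null, and from 0.94% to 1.10% under the projected effect. Multiplying θ by 0.971 as well restores 51.6% and 0.94%.

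**The case against.** The strongest reply is that nothing the plan promises fails. It claims about 91% power for the adaptive design, and the printed statistic delivers 90.5–90.9%. The 2.5% is a ceiling, Table 3 already reports 2.0%, and 1.4–1.7% respects it. The 560 maximum was justified by simulation on a standardized normal scale, and nothing shown here ties it, the interim timing or the bounds to the variance behind 376. All of that stands.

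A reader might infer more, and the documents do not support it:
- **That the trial is underpowered or its error control is broken.** It is not; the error is in the conservative direction.
- **That power at 376 is really 88.3%.** That is the formula value. Simulation puts the loss at about 1 point, to about 89.3%.
- **That the plan demonstrably used two different variances.** No formula for 376 is printed. Other calculations give 366, 369, 382 or 384, within 3% of the stated figure, though only the tie-corrected formula matches exactly.
- **That the 0.34 effect requires the tie correction.** Direct conversion gives 0.09375×√(12/0.9421) = 0.335 with ties and 0.325 without. The plain difference in mean mRS over the pooled SD is 0.59/1.710 = 0.345. The plan does not say how 0.34 was obtained.

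The conservatism also depends on midranks, which the plan does not specify. Appendix B defers the rationale to a cited paper that is not part of the documents.

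**Conclusion.** The point holds as a minor technical correction. Assuming midranks and the projected distributions, the printed variance is too large: the correct value is about 0.94 of it (0.91 under the medical-arm distribution). Z is about 3% too small in the pooled case. The cost is about 1.5 to 2 points of adaptive power, about 10 patients in expected sample size, and a type I error further below its ceiling than intended. The plan's stated power, error ceiling and maximum sample size are not violated. The inconsistency with 376 is a well-supported inference, because the tie-corrected formula gives 375.4 and the no-ties formula 398.5, but it is not a demonstrated fact. Because the factor depends on how outcomes are distributed in the population tested, the shrinkage will vary somewhat between looks and nested subgroups.

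**What to change.** In Appendix B:
1. State that tied mRS scores receive midranks.
2. Multiply the variance in both Z and Z-tilde by 1 − Σ(t³ − t)/(N³ − N), where t are the tie counts and N the number of patients in the population being tested.
3. Put θ on the same scale by multiplying it by the square root of the projected tie factor: 0.0791 × 0.971 = 0.0768, with the same rescaling of the relaxed θ after subgroup selection. Without this step the futility and enrichment bound is crossed slightly more often.
4. Confirm b, b-tilde and c by simulation on the corrected scale before any unblinded look. The runs above indicate that they can stay, with type I error below 2.5%.
5. In Section 6.1, print the formulas behind 376 and 0.34.

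The cost is one term in two formulas, one rescaled constant and a repeat of the design simulation. No additional patients are needed.

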Appendix C. List of Approved Devices to be used in the SELECT2 Protocol:

Stent-Retriever Devices:

1. K173352 - Trevo ProVue Retriever and Trevo XP ProVue Retriever
2. K162539 - Solitaire 2 Revascularization Device
3. K173452 - EmboTrap II Revascularization Device
4. K203219 - Trevo XP ProVue Retriever, Trevo NXT ProVue Retriever
5. K193576 - Solitaire Platinum and Solitaire X Revascularization Devices
6. K193063 - Embotrap III Revascularization Device
7. K203592 - Tigertriever and Tigertriever 17 Revascularization Device

Aspiration Devices:

1. K173761 - Penumbra System (Reperfusion Catheter JET 7)
2. K173200 - SOFIA Plus Aspiration Catheter
3. K183464 - AXS Universal Aspiration System
4. K191768 - AXS Vecta Aspiration System
5. K190338 - Zenith Flex Aspiration System
6. K193380 - Cerenovus Large Bore Catheter; Cerenovus Aspiration Tubing Set
7. K201689 - Riptide Aspiration System
8. K202182 - ZOOM Reperfusion Catheters; ZOOM Aspiration Tubing
9. K211476 - ZOOM 71 Reperfusion Catheter; ZOOM Aspiration Tubing
